10.2 Clinical Site Monitoring

The MRC Clinical Trials Unit will be responsible for monitoring the ORTU and the ORTU will monitor all other recruiting sites as per Monitoring Plan. Primary source data checks of a subset of information will be performed in a subset of patients according to the Monitoring Plan based on the trial Risk Assessment developed by ORTU.

10.3 Direct Access to Data

Principal Investigators at the recruiting centres will facilitate access to trial records for the purpose of monitoring, audits and ethic committee reviews. We will obtain participants' consent for this at the time of randomisation.

10.4 Confidentiality

Full medical confidentiality will be preserved. The WMA Helsinki Declaration (Amended October 2008) is accepted as the basis for conducting this trial.

Investigators at the recruiting centre will sign an agreement agreeing to adhere to this protocol and stating their responsibilities. Participants' personal identification will not be disclosed. Patients involved in this trial will be identified by initials and trial number on all CRFs. Stored specimens at Oxford will only identify patients by trial number. Patients will not be individually identified in any results publications.

10.5 Quality Assurance

Quality Assurance: This will be a randomised, controlled trial. All appropriate ethical approvals will be obtained. A register of screened patients will be kept. Randomisation (with minimisation) will be by central computer derived allocation. A Trial Steering Committee with an independent Chair and additional independent members will have oversight of the study. The Trial Steering Committee and IDMC will review the final report. Safety data will be reviewed by the IDMC. The protocol will be submitted to the MRC Clinical Trials Unit Protocol Review Committee.

Quality Control: Data validation of primary data will include at least confirmation of patient identity, informed consent, eligibility criteria, treatment compliance, and primary outcome data. Protocol delivery will be managed according to Standard Operating Procedures governing the performance of the Clinical Trials Units.

11. ADVERSE EVENTS AND REACTIONS

CPAP therapy for OSAHS has been extensively used in the middle-aged population and therefore its adverse event profile is generally well known. Description of this treatment's tolerability and adverse event profile in the elderly population is an important aim of this study, and there are reasons to believe older people may suffer more adverse events than middle-aged populations. For example, manual dexterity allowing comfortable mask adjustment may be reduced, and there may be increased facial skin fragility affected by the mask. Nonetheless, it is not expected that novel (unexpected) adverse device effects will be encountered, and the adverse event profile is expected to be modest. Therefore, the pattern of adverse event reporting is tailored to the needs of this study and is restricted compared to the general ICH E2A description.

11.1 Adverse Event (AE)

An AE or adverse event is any untoward medical occurrence in a patient or other clinical investigation participant taking part in a trial of a medical device, which does not necessarily have to have a causal relationship with the device under investigation.

An AE can therefore be any unfavourable and unintended sign (including an abnormal laboratory finding), symptom or disease temporally associated with the use of the device, whether or not considered related to the device.

11.1.1 Serious Adverse Event (SAE):

A Serious Adverse Event (SAE) is an adverse event that:

- Led to death
- Led to foetal distress, foetal death or congenital abnormality or birth defect
- Led to serious deterioration in the health of the subject that

- Resulted in a life-threatening illness or injury NOTE: The term "life-threatening" in the definition of "serious" refers to an event in which the participant was at risk of death at the time of the event; it does not refer to an event which hypothetically might have caused death if it were more severe.
- o Resulted in a permanent impairment of a body structure or a body function
- o Required in-patient hospitalisation or prolongation of existing hospitalisation
- Resulted in medical or surgical intervention to prevent permanent impairment to a body structure or a body function
- Other important medical events*
 *Other events that may not result in death, are not life threatening, or do not require hospitalisation, may be considered a serious adverse event when, based upon appropriate medical judgement, the event may jeopardise the patient and may require medical or surgical intervention to prevent one of the outcomes listed above

To ensure no confusion or misunderstanding of the difference between the terms "*serious*" and "*severe*", which are not synonymous, the following note of clarification is provided:

The term "*severe*" is often used to describe the intensity (severity) of a specific event (as in mild, moderate, or severe myocardial infarction); the event itself, however, may be of relatively minor medical significance (such as severe headache).

This is not the same as "*serious*," which is based on patient/event outcome or action criteria usually associated with events that pose a threat to a participant's life or functioning. Seriousness (not severity) serves as a guide for defining regulatory reporting obligations.

11.2 Adverse Device Effect (ADE)

Adverse Device Effects (ADEs) are all untoward and unintended responses to a medical device.

The phrase "responses to a medical device" means that a causal relationship between the device under investigation and an AE is at least a reasonable possibility, i.e., the relationship cannot be ruled out.

All cases judged by either a medically qualified professional or the sponsor as having a reasonable suspected causal relationship to the device qualify as a device effect.

This also includes any event resulting from insufficiencies or inadequacies in the instruction for use or deployment of the device and includes any event that is a result of a user error.

11.2.1 Expected Adverse Device Effects

CPAP therapy is generally very well tolerated. The main expected adverse device effects on CPAP therapy are:

- nasal dryness/discomfort
- nasal discharge
- mouth drying and dribbling
- facial soreness/discomfort
- occasional facial ulceration due to poor mask fitting

These adverse device effects can be minimised by the use of humidification and careful mask fitting. All the centres recruiting to this trial have established experienced clinical services with the necessary skill set to minimise these side-effects. The frequency of these adverse device effects will be recorded on the case report forms (CRFs).

11.2.3 Serious Adverse Device Effects (SADE)

A Serious Adverse Device Effect (SADE) is any untoward medical occurrence seen in a patient that can be attributed wholly or partly to the device which resulted in any of the characteristics or lead to the characteristics of a Serious Adverse Event.

SADE is also any event that may have led to these consequences if suitable action had not been taken or intervention had not been made or if circumstances had been less opportune. SADE will be documented on an SAE form.

11.2.4 Unanticipated Adverse Device Effect (UADE)

An Unanticipated Adverse Device Effect (UADE) is any Serious Adverse Device Effect on health or safety or any life-threatening problem or death caused by, or associated with a device, if it was not previously identified in nature, severity or degree of incidence in the investigational plan or application (including a supplementary plan or application). It can also be any other unanticipated serious problem associated with a device that related to the rights, safety or welfare of the subject.

Unexpected Adverse Device Effects will be documented on an SAE form. The probability of Unexpected Adverse Device Effect is low.

11.3 Recording of Adverse Events

CPAP therapy has been very extensively used in middle-aged patients. Its adverse event profile in that group is well described. The pattern/severity of the expected adverse events may differ in the study population in this trial, but novel (unexpected) adverse device effects are not likely.

For this trial, Adverse Events will be recorded systematically during the CPAP set-up and during the 12 months of the follow-up. Adverse Event recording will include any adverse event having a reasonable possibility of being attributable to the trial (that is an Adverse Device Effect) **and** any other Adverse Event considered to be of medical interest/importance by the local Principal Investigator. Adverse Events should be recorded on the routine CRFs.

All Adverse Reactions that result in a patient stopping treatment early, or are present at the end of the study should be followed up until a satisfactory resolution occurs.

It will be left to the investigator's clinical judgment whether or not an Adverse Event is of sufficient severity to require the patient's removal from the trial treatment. A patient may also voluntarily withdraw from treatment due to what they perceive an intolerable Adverse Device Effect.

If either of these occurs, the patient must be given appropriate care under medical supervision until symptoms cease, or the condition becomes stable. Every effort will be made to gather outcome data on these subjects through the trial follow-up systems, or general practitioner/hospital staff unless the patient has specifically withdrawn consent to such efforts.

The secondary adverse consequences of sleepiness (the correction of which is the primary reason for using CPAP therapy for OSAHS) are recorded as trial outcomes. This particularly applies to accidents, including road accidents.

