7.3 Procedures for assessing safety

Details of adverse event and serious adverse event reporting are presented in Section 11. Any adverse events which have occurred since the previous follow-up visit **must** be reported at the next follow-up visit; there are both structured and 'free text' spaces on the case report forms (CRF) to document adverse events.

The case report forms will specifically record deaths, side-effects of CPAP therapy (particularly nasal stuffiness and obstruction, superficial nasal soreness or ulceration), cardiovascular events such as myocardial infarction or stoke, and accidents - including road accidents.

In the case of any serious adverse event (SAE) by regulatory criteria (Section 11.2), and subject to the specific adverse event recording criteria for this trial (Section 11), the recruiting centre local Principle Investigator will report the event to ORTU in keeping with regulatory reporting timelines. ORTU will manage such events in keeping with its established Standard Operating Procedures for serious adverse event assessment/management.

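### Sections 7.3 and 11.3 set different rules for which non-serious adverse events are recorded, and the 11.3 rule uses a device-based criterion that leaves recording open to being unequal between arms

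*Protocol*

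**What the plan says.** Four parts of the protocol bear on which adverse events reach the case report form.

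- **Section 7.3** makes it mandatory to report, at the next follow-up visit, "Any adverse events which have occurred since the previous follow-up visit", in structured and free-text spaces. It sets no attribution condition. It also opens with a pointer: "Details of adverse event and serious adverse event reporting are presented in Section 11".
- **Section 11.1** defines an adverse event as any untoward occurrence, "whether or not considered related to the device".
- **The introduction to section 11** says that "the pattern of adverse event reporting is tailored to the needs of this study and is restricted compared to the general ICH E2A description". It also says that "Description of this treatment's tolerability and adverse event profile in the elderly population is an important aim of this study".
- **Section 11.3** says recording on the routine CRFs will include two classes. The first is "any adverse event having a reasonable possibility of being attributable to the trial (that is an Adverse Device Effect". The second is "any other Adverse Event considered to be of medical interest/importance by the local Principal Investigator".

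Section 11.2 supplies the definition behind the first class: "Adverse Device Effects (ADEs) are all untoward and unintended responses to a medical device".

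Other items do not pass through the 11.3 filter. Section 7.3 lists deaths, CPAP side-effects, cardiovascular events and accidents as specific CRF items. Section 11.4 has SAEs unrelated to CPAP documented on SAE forms. The monthly diary (section 1.2.6 flowchart, Table 1) asks about treatment side effects.

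**The concern.** A site can follow either section and record different events. Under 7.3 a minor symptom is reported in any patient. Under 11.3 it is recorded if it may be due to the device, or if the local investigator thinks it important.

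The device criterion is the statistical problem, because exposure to the device is what randomisation assigns. Section 11.2 sets a low bar for a CPAP user: causation need only be impossible to rule out. A patient without CPAP cannot meet the criterion at all. Patients know their allocation, and section 6.4 accepts that assignment cannot be concealed, so attribution can follow knowledge of the arm.

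Two uses of the data are at stake. The tolerability profile in older people is a declared aim. The IDMC reviews adverse events after each 100 patients randomised (section 9.4), and its advice to stop may rest on a net safety difference between treatments (section 7.6). An imbalance produced by the recording rule could be read there as harm from CPAP.

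**Working it through.** **Step 1: can both rules hold?** If 7.3 governs, every adverse event is reported and the two classes in 11.3 have no function. If 11.3 governs, the unrestricted and mandatory wording of 7.3 is wrong. The pointer to section 11 does not settle this, because 7.3 goes on to state its own rule.

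**Step 2: how does a non-serious event outside the separately collected items enter under 11.3?**

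| Patient | Device-based class | Investigator-selected class |
|---|---|---|
| Using CPAP | open | open |
| Best Supportive Care, not using CPAP | closed | open |
| Best Supportive Care, switched to CPAP (section 8d) | open after the switch | open |

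No section makes the first class neutral between arms. The expected device effects in section 11.2.1 include nasal discharge and mouth drying, symptoms that can also occur without CPAP.

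**Step 3: size.** The protocol gives no adverse event rate, so there is no stated figure to reproduce and everything below is assumption. The only protocol input is 270 patients randomised 1:1 (section 9.3.1), that is 270/2 = 135 per arm. The true incidence is taken as equal in both arms. The test is a two-sided 5% comparison of two proportions; the protocol plans no such test, and it serves only to scale the artefact.

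*Illustration A.* All events are recorded on CPAP and a fraction c in control. With true incidence p, the recorded difference is p(1 − c).

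| p | c = 75% | c = 50% | c = 25% |
|---|---|---|---|
| 10% | 10.0 v 7.5%; 11% | 10.0 v 5.0%; 34% | 10.0 v 2.5%; 72% |
| 20% | 20.0 v 15.0%; 19% | 20.0 v 10.0%; 63% | 20.0 v 5.0%; 97% |
| 30% | 30.0 v 22.5%; 29% | 30.0 v 15.0%; 84% | 30.0 v 7.5%; above 99% |

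Each cell gives the recorded rates (CPAP v control), then the chance of nominal significance. At c = 100% there is no artefact.

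*Illustration B.* A fraction i of events is judged of interest in either arm, and a fraction a on CPAP is called possibly attributable, independently of i. The control rate is t·i, the CPAP rate is t[1 − (1 − i)(1 − a)], and the difference is t·a·(1 − i), where t is the true incidence.

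- Low end (t = 0.3, i = 0.6, a = 0.1): control 0.3 × 0.6 = 18.0%; CPAP 0.3 × (1 − 0.4 × 0.9) = 19.2%; difference 1.2 points. The chance of a significant excess on CPAP is about 4.4%, against 2.5% with no artefact. Counting either direction it is about 6%, against 5%.
- High end (t = 0.5, i = 0.3, a = 0.25): control 0.5 × 0.3 = 15.0%; CPAP 0.5 × (1 − 0.7 × 0.75) = 23.75%; difference 8.75 points. The chance of a significant excess on CPAP is about 44%.

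The direction is the same throughout. The size depends on site behaviour that the protocol does not fix.

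**The case against.** The strongest defence is that 7.3 sets the timing (report at the next visit) and section 11 sets the scope. Section 7.3 points there, and the restriction is deliberate and reasoned, for a device whose adverse event profile is well described. This softens the conflict. It does not remove it, because 7.3 states a mandatory rule without limit and nothing there subordinates it to 11.3. The choice to restrict may well be legitimate; the weakness is that the criterion depends on the arm.

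A reader might infer three stronger things that the protocol does not support.

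- *That 11.3 shuts out everything else.* It says recording will include the two classes, and the items most relevant to a stopping decision (deaths, SAEs, cardiovascular events) are collected without the attribution filter. Accidents are a secondary endpoint, so an accidental fall at home would be captured in either arm.
- *That a device effect cannot arise in the control arm.* Section 8d keeps control patients who switch to CPAP in follow-up.
- *That recorded rates must differ between arms.* The investigator-selected class is open to both arms and could in principle capture every control event.

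It is also fair that the declared aim is descriptive and concerns CPAP, that the non-serious event rate is not a listed endpoint, and that the protocol plans no test of it. This limits the consequence mainly to the by-arm picture put before the IDMC and any comparison in the report.

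**Conclusion.** The concern holds in a limited form. Sections 7.3 and 11.3 conflict on which non-serious adverse events are recorded. The 11.3 rule contains a criterion that only CPAP users can meet. For non-serious events outside the separately collected items, recording is therefore open to being unequal, with a tendency to over-record on CPAP. This is a risk of differential ascertainment, not a certain difference.

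Its size cannot be derived from the protocol. Under the assumed rates the artefact ranges from none (full capture in control) through about 1 to 9 percentage points (illustration B) to more than 20 points (illustration A, 30% incidence and 25% capture in control). These figures show only that the artefact could matter at 135 per arm; they do not predict it. The conclusion rests on the wording of the two sections and does not depend on the illustrations.

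**What to change.** Choose one of two options and make 7.3 and 11.3 agree.

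1. **One arm-neutral rule.** At each scheduled contact, record adverse events in both arms by the same question, whatever the suspected cause. Keep relationship to treatment (section 11.6) as a separate field, and tabulate Adverse Device Effects for CPAP users from it. Cost: a paragraph in 11.3 and a few more CRF entries.
2. **Keep the deliberate restriction and limit its use.** Amend 7.3 to refer to 11.3 for scope. State that between-arm safety comparisons and IDMC tables by arm use only items collected identically in both arms: deaths, SAEs, cardiovascular events, accidents, and diary side-effect items where the same question is put to both arms. Describe events recorded under 11.3 for CPAP users without comparison. Cost: wording only.

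The second option respects the protocol's stated reason for restricting recording and is enough to remove the problem.

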11.4 Reporting of Serious Adverse Events

Subject to the specific reporting procedures for this trial, a Serious Adverse Event (SAE) occurring to a research participant should be reported to the main REC and the Sponsor (via the ORTU) where in the opinion of the Chief Investigators, in discussion with the ORTU, the event was:

1. 'Related' – that is, it resulted from administration of any of the research procedures (Serious Adverse Device Effect) **and**

2. 'Unexpected' – that is, the event is not expected from the known characteristics of the trial intervention or the patient's clinical situation

Serious Adverse Events (related and unexpected) should be reported to the ORTU by the Principal Investigator at a recruiting site within **one working day of awareness**. The ORTU will assess this event and report the event to the main REC and the Sponsor within 15 days of the CI becoming aware of the event. The following attributes are recorded by the investigator: description, date of onset and resolution date, severity, assessment of relatedness to study intervention, other suspect drug or device and action taken.

The ORTU assessment will consist of a review of the completed Serious Adverse Event form by a medical reviewer from within ORTU with specific expertise in respiratory disease. Where the study participant has been under the care of the PI (Oxford site only), this review will be by one of the Chief Investigators, or a consultant respiratory physician from the Oxford Centre for Respiratory Medicine working under the relevant ORTU SOP.

Other adverse events which are 'serious' by the criteria specified in section 11.1.1 but are unrelated to the CPAP treatment will be documented on the SAE forms but will not be reported to the REC or the Sponsor. Submission of these SAEs to ORTU is not subject to specific timelines.

A list of all Serious Adverse Events which have occurred during the study will be kept at ORTU and provided to the manufacturers of CPAP machines - ResMed (UK) Ltd within three months of the end of the study. It will be clearly stated whether SAEs, in the opinion of the local Principle Investigator, are related to the study treatment.

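### Section 11.4 uses a narrower test of unexpectedness than 11.2.4 and never mentions UADEs, so an event that triggers IDMC contact can miss expedited reporting to the Sponsor and REC

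*Protocol*

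**What the plan says.** Section 11.2 treats an event as a device effect when "a causal relationship between the device under investigation and an AE is at least a reasonable possibility, i.e., the relationship cannot be ruled out". It adds: "All cases judged by either a medically qualified professional or the sponsor as having a reasonable suspected causal relationship to the device qualify" as such. Section 11.2.1 names five main expected effects, all nasal, oral or facial. Section 11.2.3 defines a Serious Adverse Device Effect (SADE) as "any untoward medical occurrence seen in a patient that can be attributed wholly or partly to the device" with a serious outcome.

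Section 11.2.4 makes such an effect a UADE "if it was not previously identified in nature, severity or degree of incidence in the investigational plan" or in an application. The only handling step given there is completion of an SAE form. Under section 9.4, the trial statistician contacts the IDMC after any UADE and considers whether an extra meeting is needed.

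Section 11.4 sets the rule for the REC and Sponsor. An SAE goes to them when the Chief Investigators, in discussion with the ORTU, hold that "it resulted from administration of any of the research procedures" (with SADE added in brackets) and that "the event is not expected from the known characteristics of the trial intervention or the patient's clinical situation". For events meeting both conditions, the site has one working day to tell the ORTU, and the ORTU has 15 days to tell the REC and Sponsor. Other events that are serious "but are unrelated to the CPAP treatment will be documented on the SAE forms but will not be reported to the REC or the Sponsor", and sites have no deadline for submitting them.

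**The concern.** Two sections decide whether a serious device effect is a surprise, and they measure it differently. Section 11.2.4 asks whether the plan had identified the event in kind, severity and frequency. Section 11.4 drops that comparison and adds a ground for calling the event expected: the patient's clinical situation. In patients aged 65 or over that ground has wide reach, because section 4 says that cardiac and cerebrovascular disease is to be expected in this population.

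At stake is whether a serious event with a possible device link reaches the Sponsor and REC, and how fast. Section 11 calls the description of tolerability and adverse events in the elderly an important aim. It also gives reasons why older people may have more such events, among them fragile facial skin.

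**Working it through.** No arithmetic applies. The check sets the rules side by side and takes example events through them.

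| Question | Definitions (11.2 to 11.2.4) | Reporting rule (11.4) |
|---|---|---|
| What is expectedness judged against? | The plan or application | Known characteristics of the intervention, or the patient's condition |
| Do severity and frequency count? | Yes, both named | Neither named |
| What causal link is needed? | One that cannot be ruled out | The event resulted from the procedure, with SADE in brackets |
| Who judges? | A medically qualified professional or the sponsor | Chief Investigators with the ORTU |
| Are UADEs mentioned? | Defined in 11.2.4 | No |

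**Example 1: serious cardiac event on CPAP, known heart disease, device link not ruled out.**
1. Under 11.2 and 11.2.3 it can be a SADE.
2. Nothing of this kind is among the effects named in 11.2.1. Unless it is identified elsewhere in the plan or an application, it is a UADE under 11.2.4.
3. Under 9.4 the statistician contacts the IDMC.
4. Under 11.4 it can be judged expected from the patient's clinical situation. The second condition then fails, and the duty to report to the REC and Sponsor does not arise, nor do the two time limits.

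**Example 2: facial ulceration serious enough for admission.**
1. Section 11.2.1 names occasional facial ulceration, so the kind of event is identified.
2. If the severity exceeds what the plan identified, 11.2.4 can still make it a UADE.
3. Under 11.4 it can be called expected from the known characteristics of CPAP, because severity is not part of that test. Yet 11.3 says the severity of expected events may differ in this population.

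**The gap between the rules.** 11.4 requires reports of serious events that are related and unexpected, and excludes those unrelated to CPAP. It says nothing about those that are related but expected, and both examples can end there.

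**Two lesser ambiguities in 11.4.**
- The wording of the relatedness condition, "it resulted from administration of any of the research procedures", is stricter than the 11.2 threshold, "is at least a reasonable possibility, i.e., the relationship cannot be ruled out". The bracketed SADE term beside it may import that threshold, but the text does not say so.
- The first condition covers any research procedure, whereas the exclusion speaks only of events unrelated to CPAP. The place of a serious injury during a trial test is left to interpretation.

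**The case against.** The strongest defence is that the restriction is deliberate. Section 11 says that adverse event reporting is tailored to this study and is narrower than the general ICH E2A description. A wide trigger for the IDMC and a narrower one for the Sponsor and REC is not in itself an error. There are also safeguards. Unrelated SAEs still go on SAE forms, the ORTU keeps a list of all SAEs, and the IDMC reviews outcomes and adverse events at every hundred randomisations. Deaths are specifically recorded (7.3), and cardiovascular events are prespecified outcomes (9.2.2). This stands as far as it goes: the events are not lost to the trial, and its description of safety in older people does not depend on expedited letters. But a general statement of restriction does not say which of two tests governs a UADE, and none of these safeguards supplies an expedited route to the Sponsor and REC.

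A reader might infer more than the text supports:
- *That 11.4 plainly contradicts the causal threshold of 11.2.* The bracketed SADE is a defined term under 11.2, so the threshold is plausibly carried over. This is an ambiguity.
- *That a fall during the Timed Up and Go test is both reportable and barred.* The exclusion opens by speaking of other events, so it can be read as covering only what the main rule has not caught.
- *That every cardiovascular or respiratory device effect is unanticipated, and nearly all can be called expected under 11.4.* Section 11.2.1 lists only the main expected effects, and 11.2.4 looks to the whole plan or application. No count supports either claim.
- *That sites will settle the same event in opposite ways.* Sites make the first screen, but the decision on reporting to the REC and Sponsor is central.

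**Conclusion.** The point holds for expectedness. On the text of 9.4, 11.2.4 and 11.4, a serious device effect can be a UADE that brings in the IDMC and yet fall outside the reporting rule for the Sponsor and REC and its two time limits. The cause is a narrower test of unexpectedness in 11.4, together with its silence on UADEs and on related-but-expected SAEs. The questions about the causal threshold and about research procedures are secondary ambiguities.

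The size cannot be put in numbers: the protocol gives no rate for such events, and how often the patient's condition would be invoked is unknown. The conclusion assumes that 11.4 is applied as written and that no charter or operating procedure outside the protocol already closes the gap. It concerns safety reporting only and leaves the endpoints, the sample size of 270, power and analysis untouched. It should be put right because the events that can slip through are serious ones with a possible device link.

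**What to change.** Reconcile 9.4, 11.2, 11.2.4 and 11.4:

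1. **Expectedness and UADEs.** In 11.4, define unexpected by reference to 11.2.4: not identified in the plan in nature, severity or incidence. For device-related events, remove the patient's clinical situation as a ground for calling an event expected. State that every UADE follows the 11.4 expedited route to the ORTU, Sponsor and REC. Add a sentence saying how related-but-expected SAEs are handled.
2. **Relatedness.** State that *related* in 11.4 carries the 11.2 threshold.
3. **Scope of the exclusion.** Change it from events unrelated to the CPAP treatment to events unrelated to CPAP or any research procedure.

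The cost is a wording amendment and a note to sites. There may be a few more expedited reports; their number is unknown.
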